12.1 Determination of Sample Size

A sample size of 52 patients will have 80% power to detect a change from baseline to Week 5 of at least 0.35 points in the Wound-QoL global score (e.g., a baseline mean Wound-QoL global score of 3.53 and a follow-up mean Wound-QoL global score of 3.18), assuming an estimated SD of differences of 0.88, using a paired t-test with a 0.050 two-sided significance level. Patients who withdraw or are withdrawn before completion of the Week 2 assessments and the Week 3 Wound-QoL questionnaire will be replaced to ensure that at least 52 patients will complete the study.

12.2 Analysis Population

All patients who receive at least 2 weeks of study treatment and complete the Week 3 Wound-QoL questionnaire will be included in the primary analysis population used for all analyses. Additional populations may be explored and will be detailed in the SAP.

12.3 Disposition

Patient disposition will be summarized in terms of the number of patients who enter the study, the number who discontinue early, the number who complete the study and the number who are included in each relevant subgroup or baseline category.

12.4 Demographic and Baseline Characteristics

Demographic variables to be recorded include age, race, ethnicity, gender, body height, and body weight. Wound history to be recorded includes wound type(s), wound age(s), location(s), past complications, and current dressing change frequency. Also, screening length and width of the wound(s) will be recorded.

Demographic and baseline information will be summarized in tables using descriptive statistics.

12.5 Clinical Outcome Analyses

The global score of the Wound-QoL questionnaire will be summarized and explored in several ways. The primary analysis will be a paired t-test analysis of the mean global score of the Wound-QoL questionnaire at baseline and after 4 weeks of treatment. The global score of the Wound-QoL questionnaire may also be categorized to describe the proportion of patients with particular scores on individual questions, such as those with no score of 3 or 4 given, or to split the possible results into categories.

Secondary analyses include the changes from baseline in the subscores of the Wound-QoL questionnaire for the Body, Psyche, and Everyday Life QoL dimensions.

Exploratory analysis includes the change from baseline in the appearance and size of the wound(s).

All endpoints will be summarized using descriptive statistics.

Subgroup analyses may be performed based on such things as the size of the wound(s), the duration of treatment application, and the type of wound(s).

12.6 Safety Analysis

All reported AEs will be coded using the Medical Dictionary for Regulatory Activities. The incidence of TEAEs (events with onset dates on or after the start of the study treatment) will be included in incidence tables. Events with missing onset dates will be included as treatment-emergent. If a patient experiences more than 1 occurrence of the same AE, the occurrence with the greatest severity and the closest association with the study device will be used in the summary tables. SAEs, AEs causing discontinuation, and ADEs will be tabulated. All AEs will be listed by patient, along with information regarding onset,

duration, severity, relationship to study device, action taken with study device, treatment of event, and outcome.

Clinical laboratory data, vital signs, physical examination results, wound history, and medical history will be listed by patient.

Listings and summary tables will be provided for prior medications and for concomitant medications initiated or continued during the study period. Study treatment exposure will be listed by patient and summarized descriptively.

13 STUDY MANAGEMENT

13.1 Study-Specific Materials

In addition to the Study Products, the Sponsor will also supply the following items for this study:

1. Single-use, disposable rulers for wound measurements
2. Pens for marking bottles of Prontosan solution and Prontosan gel
3. Digital camera (with memory card) for wound size and appearance documentation

In addition, the study site will supply the patients with appropriate wound care materials (e.g., gauze, bandages, tape) for the care of their wound(s) while they are at home.

13.2 Approval and Consent

13.2.1 Regulatory Guidelines

This study will be conducted in accordance with the accepted version of the Declaration of Helsinki and/or all relevant federal regulations, as set forth in Parts 50, 56, 312, Subpart D, of Title 21 of the Code of Federal Regulations (CFR), and in compliance with good clinical practice (GCP) guidelines.

13.2.2 Institutional Review Board

Conduct of the study must be approved by an appropriately constituted IRB. Approval is required for the study protocol, any protocol amendments, and ICFs.

13.2.3 Informed Consent

For each study patient, written informed consent will be obtained prior to performing any protocol-related activities. As part of this procedure, the Investigator or designee must explain orally and in writing the nature, duration, and purpose of the study, and the action of the study treatment in such a manner that the patient is aware of the potential risks, inconveniences, or adverse effects that may occur. The patient should be informed that he/she may withdraw from the study at any time, and the patient will receive all information that is required by the FDA and International Council for Harmonization guidelines. The Investigator will provide the Sponsor or its representative with a copy of the IRB-approved ICF prior to the start of the study.

13.3 Data Handling

Any data to be recorded directly on the eCRFs (to be considered as source data) will be identified at the start of the study. Data reported on the eCRF that are derived from source documents should be consistent with the source documents, or the discrepancies must be explained.

Clinical data will be entered on eCRFs for transmission to the Sponsor. Data on eCRFs transmitted via the web-based data system must correspond to and be supported by source documentation maintained at the study site, unless the study site makes direct data entry to the databases for which no other original or source documentation is maintained. In such cases, the study site should document which eCRFs are subject to direct data entry and should have in place procedures to obtain and retain copies of the information submitted by direct data entry (such as diaries). All study forms and records transmitted to the Sponsor must carry only coded identifiers such that personally identifying information is not transmitted. The primary method of data transmittal is via the secure, internet-based EDC system maintained by inVentiv Health Clinical. Access to the EDC system is available to authorized users via the study's Internet web site, where an assigned username and password are required for access.

Any changes made to data after collection will be made through the use of data clarification forms. eCRFs will be considered complete when all missing and/or incorrect data have been resolved.

13.4 Source Documents

Source documents are considered to be all information in original records and certified copies of original records of clinical findings, observations, data or other activities in a clinical study necessary for the reconstruction and evaluation of the study.

13.5 Record Retention

Study records and source documents will be maintained per local laws and regulations.

The Investigator agrees to comply with all applicable federal, state, and local laws and regulations relating to the privacy of patient health information, including, but not limited to, the Standards for Individually Identifiable Health Information, 45 CFR, Parts 160 and 164 (the Health Insurance Portability Accountability Act of 1996 [HIPAA] Privacy Regulation). The Investigator shall ensure that study patients authorize the use and disclosure of protected health information in accordance with HIPAA Privacy Regulation and in a form satisfactory to the Sponsor.

13.6 Monitoring

The study will be monitored to ensure that it is conducted and documented properly according to the protocol, GCP, and all applicable regulatory requirements.

On-site monitoring visits may be made on a "for cause" basis for quality purposes. Clinical monitors must have direct access to source documentation in order to check the completeness, clarity, and consistency of the data recorded in the eCRFs for each patient.

The Investigator will make available to the clinical monitor source documents and medical records necessary to complete eCRFs. In addition, the Investigator will work closely with the clinical monitor and, as needed, provide them appropriate evidence that the conduct of the study is being done in accordance with applicable regulations and GCP guidelines.

13.7 Quality Control and Quality Assurance

The Sponsor or its designee will perform the quality assurance and quality control activities of this study; however, responsibility for the accuracy, completeness, and reliability of the study data presented to the Sponsor lies with the Investigator generating the data.

The Sponsor may arrange audits as part of the implementation of quality assurance to ensure that the study is being conducted in compliance with the protocol, standard operating procedures, GCP, and all applicable regulatory requirements. Audits will be independent of and separate from the routine monitoring and quality control functions. Quality assurance procedures will be performed at study sites and during data management to assure that safety and efficacy data are adequate and well documented.

13.8 Protocol Amendment and Protocol Deviation

13.8.1 Protocol Amendment

Amendments to the protocol that entail corrections of typographical errors, clarifications of confusing wording, changes in study personnel, and minor modifications that have no impact on the safety of patients or the conduct of the study will be classed as administrative amendments and will be submitted to the IRBs for information only. The Sponsor or its designee will ensure that acknowledgement is received and filed. Amendments that are classed as substantial amendments must be submitted to the IRBs for approval.

13.8.2 Protocol Deviations

Should a protocol deviation occur, the Sponsor or its designee must be informed as soon as possible. Protocol deviations and the reasons they occurred will be included in the clinical study report. Reporting of protocol deviations to the IRB and in accordance with applicable FDA mandates is an Investigator responsibility.

13.9 Ethical Considerations

This study will be conducted in accordance with the accepted version of the Declaration of Helsinki and/or all relevant federal regulations, as set forth in Parts 50, 56, 312, Subpart D, of Title 21 of the CFR, and in compliance with GCP guidelines.

IRBs will review and approve this protocol and the ICF. All patients are required to give written informed consent prior to participation in the study.

13.10 Financing and Insurance

Prior to the study commencing, the Sponsor or its designee and the Investigator (or the institution, as applicable) will agree on costs necessary to perform the study. This agreement will be documented in a financial agreement that will be signed by the Investigator (or the institution signatory) and the Sponsor or its designee.

The Investigator is required to have adequate current insurance to cover claims for negligence and/or malpractice. The Sponsor will provide insurance coverage for the clinical study as required by national regulations.

13.11 Publication Policy

Both the use of data and the publication policy are detailed within the clinical study agreement. Intellectual property rights (and related matters) generated by the Investigator and others performing the clinical study will be subject to the terms of a clinical study agreement that will be agreed between the Institution and the Sponsor or its designee. With respect to such rights, the Sponsor will solely own all rights and interests in any materials, data, and intellectual property rights developed by Investigators and others performing the clinical study described in this protocol, subject to the terms of any such agreement. In order to facilitate such ownership, Investigators will be required to assign all such inventions either to their Institution or directly to the Sponsor or its designee, as will be set forth in the clinical study agreement.

15 APPENDICES

Appendix 1: Wound-QoL Questionnaire

The Wound-QoL questionnaire (shown below) measures the health-related QoL of patients with chronic wounds.^{14,15}

The following questions are designed to find out how your chronic wound(s) affect(s) your quality of life.

Please check one box per line!

In the last seven days ...		not at all	a little	moderately	quite a lot	very much
1	...my wound hurt					
2	...my wound had a bad smell					
3	...the discharge from the wound has upset me					
4	...the wound has affected my sleep					
5	...the treatment of the wound has been a burden to me					
6	...the wound has made me unhappy					
7	...I have felt frustrated because the wound is taking so long to heal					
8	...I have worried about my wound					
9	...I have been afraid of the wound getting worse or of getting new wounds					
10	...I have been afraid of hitting the wound against something					
11	...I have had trouble moving around because of the wound					
12	...climbing stairs has been difficult because of the wound					
13	...I have had trouble with everyday activities because of the wound					
14	...the wound has limited my recreational activities					
15	...the wound has forced me to limit my contact with other people					
16	...I have felt dependent on help from others because of the wound					
17	...the wound has been a financial burden to me					

Appendix 2: Wound Measurement with the Clock Method

Wounds are to be measured using the clock method with the standard, single-use, disposable rulers. With this technique, you will draw an imaginary box around the wound at the longest length and the greatest width of the wound, using the body orientation as an imaginary clock (12:00 is at the head, 6:00 is at the feet). Do not slant the ruler to accommodate the greatest measurement, and remember that sometimes length is smaller than width. You will measure the length and width, in centimeters (cm), of the imaginary box. To measure a wound on the feet, use the heels as 12:00 and toes as 6:00.¹⁷

To measure the greatest length of the wound (regardless of shape), use the following steps:

1. Picture the face of the clock lying over the wound bed with 12:00 pointing toward the patient's head and 6:00 toward the patient's feet.
2. Locate the part of the wound that is closest to 12:00 and draw a line (in your mind) from that point straight across the body.
3. Locate the part of the wound that is closest to 6:00 and draw another line (in your mind) from that point straight across the body.
 - Now you have 2 parallel lines framing the top and bottom of the wound.
4. Place a standard, single-use, disposable ruler between these 2 parallel lines to measure the greatest length in cm.

To measure the greatest width of the wound, use the following steps:

5. Locate the part of the wound that is closest to 9:00 and draw a line (in your mind) at that point straight up and down (head to foot).
6. Locate the part of the wound that is closest to 3:00 and draw another line (in your mind) at that point straight up and down.
 - Now you have 2 parallel lines framing the left and right sides of the wound, thus completing the imaginary box around the wound.
7. Place a standard, single-use, disposable ruler between these 2 parallel lines to measure the greatest width in cm.
8. Remember to document all measurements in cm.

At this point, you have the maximum length (instructions 1 to 4) and the maximum width (instructions 5 to 7) of the wound. You can now calculate the surface area of the wound (length x width) in cm². To qualify for this study, the wound must be between 5 cm² and 50 cm², inclusive.

ADE	Adverse Device Effect
AE	Adverse Event
eCRF	Electronic Case Report Form
FDA	Food and Drug Administration
HbA1c	Glycated Hemoglobin
ICF	Informed Consent Form
IFU	Instructions for Use
MedDRA	Medical Dictionary for Regulatory Activities
PHMB	Polyaminopropyl biguanide (polyhexanide)
PT	Preferred Term
QoL	Quality of life
SAE	Serious Adverse Event
SAF	Safety Population
SAP	Statistical Analysis Plan
SAS	Statistical Analysis Software
SD	Standard Deviation
SOC	System Organ Class
SUSAR	Suspected Unexpected Serious Adverse Reaction
TEAE	Treatment-Emergent Adverse Event
TIME	Tissue, Infection/Inflammation, Moisture, Edge

1. INTRODUCTION

Chronic leg wounds are those that do not progress through the normal healing process in a timely manner. In the United States alone, these wounds are estimated to affect between 2.4 to 4.5 million patients.¹ Chronic wounds are typically classified as vascular ulcers (venous and arterial ulcers), diabetic ulcers, and pressure ulcers. As these wounds last on average 12 to 13 months and recur in up to 60% to 70% of patients, they can lead not only to a loss of function and a decreased quality of life, but also to an increase in morbidity. Primarily a condition of the elderly, chronic wounds are becoming more prevalent as populations age in developed countries and are associated with high treatment costs, estimated at 2% to 3% of the healthcare budgets in these countries.²

The physiological process of wound healing progresses through 4 main phases: hemostasis, inflammation, proliferation, and remodeling.³ Immediately after an injury, vasoconstriction and blood clotting occurs, preventing blood loss and providing a provisional matrix for cell migration. Platelets secrete growth factors, and cytokines attract endothelial cells, fibroblasts, and immune cells. The inflammation stage usually lasts up to 7 days, during which time phagocytic cells are at work: neutrophils release reactive oxygen species and proteases that prevent bacterial contamination and cleanse the wound of cellular debris, and monocytes differentiate into tissue macrophages that remove bacteria and nonviable tissue and release growth factors and cytokines. As blood vessels are repaired and immune cells undergo apoptosis, the inflammation phase winds down and the proliferation phase begins. During the proliferation phase, tissue granulation, angiogenesis, and epithelialization occur. During the remodelling phase, which begins after the wound has closed and may last 1 to 2 years or longer, the provisional matrix is remodelled into organized collagen bundles.³

Chronic wounds often stall in the inflammation phase. Although they may differ in etiology, chronic wounds usually share some common features: elevated levels of proinflammatory cytokines, proteases, reactive oxygen species, and senescent cells; persistent infection; and a deficiency of stem cells and/or dysfunctional stem cells. Repeated tissue injury induces platelet-derived factors to stimulate the constant influx of immune cells; thus, the proinflammatory cytokine cascade becomes amplified and persists for a prolonged period, leading to elevated levels of proteases. Eventually, protease levels exceed the levels of their inhibitors, leading to the destruction of the extracellular matrix and the degradation of growth factors and their receptors. The destruction of the matrix not only prevents a progression to the proliferative phase, but also attracts more inflammatory cells, amplifying the inflammation cycle. Similarly, elevated levels of reactive oxygen species also damage the extracellular matrix, which stimulates proteases and inflammatory cytokines. This amplified inflammation cycle, together with the deficiency of functional stem cells, results in a failure to achieve complete re-epithelialization in tissue repair.^{3,4}

In caring for chronic wounds, the concurrent management of both the underlying systemic problem (e.g., diabetes, peripheral arterial disease) and the wound bed preparation encourages the proper environment in which autolytic tissue repair can take place. The basic tenets of wound bed preparation have been described by the TIME acronym: Tissue assessment and management, Infection/Inflammation management, Moisture imbalance management, and Edge of wound observation and management.³ For tissue management, repetitive and maintenance debridement and wound cleaning are recognized as essential throughout the healing period. As almost all chronic wounds are thought to contain biofilms, topical antiseptics are commonly used to control bioburden in wounds. Excessive or insufficient wound exudate can be addressed with a wide range of dressings to regulate moisture balance, to protect peri-wound skin, and to optimize healing. At the edge of the wound, therapies such as negative pressure wound therapy may be used to help improve epithelial advancement and wound closure.⁵

Typically applied agents available for debridement, cleaning, and moistening acute and chronic wounds include such solutions as sterile saline, honey, povidone-iodine, cadexomer iodine, hypochlorous acid, a “super-oxidized” solution (sodium chloride/ sodium hypochlorite/ hypochlorous acid solution), collagenase, and polyhexamethylene biguanide [PHMB] (Prontosan® Wound Irrigation Solution and Prontosan® Wound Gel).^{3, 6}

2. STUDY OBJECTIVES

The primary objective of this study is to assess the overall change in the QoL after 4 weeks of treatment with Prontosan solution and Prontosan gel in patients with chronic leg wound(s). This will be determined by calculating the change from baseline in the global score of the Wound-QoL questionnaire.

The secondary objective is to assess the changes in the Body, Psyche, and Everyday Life subscores of the Wound-QoL questionnaire after 4 weeks of treatment with Prontosan solution and Prontosan gel.

The exploratory objective is to assess the change in the appearance and size of the wound(s) by direct evaluation and photographic measurements after 4 weeks of treatment with Prontosan solution and Prontosan gel.

3. STUDY DESIGN

This is a prospective, open-label, multi-site, single-arm study in patients with chronic leg wound(s). The investigator or designee will apply Prontosan solution and Prontosan gel to the wound(s) at clinical visits Week 1, Week 2, Week 5. Patients will apply Prontosan solution and Prontosan gel themselves (or have them applied by a caregiver) at home (Week 3 and Week 4). The study contains Screening period (Week 0), 4 weeks of treatment period (Week 1 – Week 5), and safety follow-up.

The schedule of assessments to be performed throughout the study is given in the protocol.

4. ANALYSIS POPULATIONS

4.1 Enrolled Population

The Enrolled Population includes all patients who signed the informed consent form at the Screening visit and met the inclusion/exclusion criteria while participating at the Week 1 visit.

4.2 Evaluable Population

The Evaluable Population includes all patients who receive at least 2 weeks of study treatment and complete the Week 3 Wound-QoL questionnaire.

The analyses of primary endpoint, secondary endpoints, and exploratory endpoints will be done in the evaluable population.

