5.2 Study Endpoints

5.2.1 Primary Endpoint

The primary endpoint of this study is the change from baseline to Week 5 in the global score of the Wound-QoL questionnaire.

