5.1.2 Handling of Dropouts and Missing Data

Patients who prematurely withdraw from the study for any reason should complete the early discontinuation visit requirements. If the early discontinuation visit is not done, the reason(s) will be recorded in the eCRF. Patients who withdraw or are withdrawn before completion of the Week 2 assessments and the Week 3 Wound-QoL questionnaire will be replaced to ensure that at least 52 patients will complete the study.

The questionnaire consists of 17 statements of impairments. The patient assesses and documents the degree to which the impairments affected him/her within the previous 7 days by ticking checkboxes using a Likert scale from 0 to 4: 0=not at all, 1=a little, 2=moderately, 3=quite a lot, 4=very much. The global score is an average of the completed questionnaire items, which can be calculated if at least 13 out of 17 items are completed.

If more than 1 box is checked within an item, or if a patient has checked between 2 checkboxes, the item is treated as missing. Missing items are not averaged in the global score. A global score can be computed only if at least 75% of the items have been answered and are not treated as discarded or as missing (at least 13 of the 17 items are valid), and a subscore (Body, Psyche, and Everyday Life) can be computed only if no more than 1 item of the subscale is missing.

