5.1.4 Time Windows

In this post-marketing study, data will be collected from each patient at screening, baseline (Week 1), Week 2, Week 3, Week 4 and Week 5 (final visit). The Week 1 baseline visit will be scheduled at ≤ 1 week after screening visit with a window of ± 1 day. For the visits Week 2 up to Week 5, a window of ± 1 day will be allowed for patient data collection.

All patients are to adhere to the visit schedule as specified in the flowchart (Table 1). If any visit or assessment has to be rescheduled and deviates from the given time window, this visit or assessment, will be handled as out of window. Subsequent visits should follow the original visit date schedule. Out of window and unscheduled assessments will be listed, but not used for descriptive analysis and calculation of primary and secondary endpoints.

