5.1.5 Patient Disposition

Patient disposition will be summarized as indicated below using the Enrolled Analysis Population. The disposition categories will be summarized by number and percentage using the number of enrolled patients as a percentage denominator:

- Enrolled patients
- Safety population
- Evaluable population
- Completer population
-

Patient disposition information will be listed. In addition, patients who were discontinued from the treatment or who did not complete the treatment will also be presented in this listing, including early termination reason. A subject is considered a statistical completer (Evaluable population) if he/she receives at least 2 weeks of study treatment and completes the Week 3 Wound-QoL questionnaire.

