5.2.1 Primary Analysis

The primary endpoint is defined as

- Change from baseline to Week 5 in the global score of the Wound-QoL questionnaire.

The primary endpoint will be analysed by the following primary analysis in the evaluable and completer populations.

Let μ be defined as expected value of change from baseline to Week 5 in the global score of the Wound-QoL questionnaire.

The null hypothesis to be tested is that μ is equal to 0, i.e., no score change from baseline. The alternative hypothesis is that μ is different from 0. i.e.:

$H_0: \mu = 0$ vs. $H_1: \mu \neq 0$.

The null hypotheses will be tested using a paired t-test statistic. The t-test is conducted using Proc MEANS procedure in SAS version 9.4. The null hypothesis will be rejected at a two-tailed significance level of 0.05.

In addition, descriptive statistics (n, mean, SD, median, min, max) will be provided in the evaluable population for the primary endpoint. Associated the 95% CI and p-value will be presented for the change from baseline to Week 5 in the global score of the Wound-QoL questionnaire.

The primary endpoint analysis will also be repeated using the safety and completer populations.

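### The lead analysis of the baseline-to-Week 5 change requires a completed Week 3 home questionnaire that the endpoint does not use

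*SAP*

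**What the plan says.** **Endpoint.** Protocol 5.2.1: "The primary endpoint of this study is the change from baseline to Week 5 in the global score of the Wound-QoL questionnaire". SAP 5.2.1 tests the mean of this change with a paired t-test. Only two scores per patient enter, baseline (the Week 1 visit) and Week 5.

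**Lead population.** SAP 4.2: "The Evaluable Population includes all patients who receive at least 2 weeks of study treatment and complete the Week 3 Wound-QoL questionnaire". It assigns the primary, secondary and exploratory endpoints to this set. Protocol 12.2 uses the same two conditions and says that such patients "will be included in the primary analysis population used for all analyses". The Week 3 form is filled in at home, as there is no clinic visit that week (Protocol 9.2.4 and Table 1).

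**Repeats.** SAP 4.3 and 4.4 repeat the primary analysis in the Safety Population (any treated patient, Table 6.5) and the Completer Population (patients completing the 4-week treatment period, Table 6.9). Neither requires the Week 3 form. One sentence of SAP 5.2.1 reads: "The primary endpoint will be analysed by the following primary analysis in the evaluable and completer populations". The section ends by listing safety and completer as repeats.

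**Replacement.** SAP 5.1.2: "Patients who withdraw or are withdrawn before completion of the Week 2 assessments and the Week 3 Wound-QoL questionnaire will be replaced". The aim is at least 52 completing patients.

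**Early discontinuation.** Protocol 9.2.5 and Table 1 footnote a place this visit under the Week 5 final visit. SAP 5.1.4 allows 1 day either side for Week 5 and says: "Out of window and unscheduled assessments will be listed, but not used for descriptive analysis and calculation of primary and secondary endpoints". It describes an out-of-window visit as one that "has to be rescheduled and deviates from the given time window", and does not name the early discontinuation visit.

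**The concern.** An analysis set for a two-point change should follow from those two points. Here an intermediate home form, which contributes nothing to the endpoint, decides who is in the lead result. A patient who was treated throughout and gave valid baseline and Week 5 scores can be excluded for something that happened after baseline. That patient has not withdrawn, so the replacement rule does not bring in anyone else.

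In a single-arm study the mean change among the analysed patients is the whole result, and the choice of set matters correspondingly. The sample size also has almost no slack, so usable pairs should not be set aside without a reason tied to the endpoint.

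A smaller, related gap is the handling of a score from an early discontinuation visit. The protocol gives that visit the Week 5 label. The SAP window rule appears to exclude the score but does not say so.

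**Working it through.** **Inputs.** Mean change 0.35, SD of differences 0.88, two-sided alpha 0.05, paired t-test, 52 patients, 80% power (SAP 5.1.3, Protocol 12.1).

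**1. The plan's own figure.** For n pairs, the noncentrality is (0.35/0.88) × √n on n − 1 degrees of freedom. Power is the probability that the noncentral t exceeds the two-sided critical value.

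- n = 52: noncentrality 0.3977 × 7.211 = 2.868, critical value 2.008, power 80.3%.
- n = 51: noncentrality 2.840, critical value 2.009, power 79.5%.

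The stated 52 at 80% is reproduced, and 52 is the smallest number that reaches 80%. The sample-size arithmetic is not at fault. It does assume 52 usable baseline-to-Week 5 pairs.

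**2. Who is in the lead test.** Take a treated patient with a valid baseline score.

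| Week 3 form | Week 5 score | Evaluable (Table 6.1) | Safety (Table 6.5) |
|---|---|---|---|
| yes | yes | pair analysed | pair analysed |
| no | yes | excluded | pair analysed |
| yes | no | in the set, no pair | in the set, no pair |
| no | no | excluded | in the set, no pair |

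Only the second row changes the t-test. The third row adds no pair under either definition.

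**3. Illustration of size.** The documents give no rate of missed Week 3 forms, so the counts below are assumptions. The 95% CI half-width is t(0.975, n − 1) × 0.88/√n.

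| Pairs lost of 52 | Pairs in lead test | Power | CI half-width |
|---|---|---|---|
| 0 | 52 | 80.3% | 0.245 |
| 1 (2%) | 51 | 79.5% | 0.248 |
| 3 (6%) | 49 | 77.9% | 0.253 |
| 5 (10%) | 47 | 76.1% | 0.258 |
| 8 (15%) | 44 | 73.2% | 0.268 |

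The plan's figure is a minimum. If enough additional patients enrol, the lead test still has 52 pairs or more.

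**4. Early discontinuation timing.** Count baseline as day 0. The Week 3 form is due on day 14 (days 13 to 15) and Week 5 is day 28 (days 27 to 29). A patient who completes the Week 3 form and has the early discontinuation visit on days 16 to 26 meets the Evaluable definition but falls outside the Week 5 window. Under SAP 5.1.4 read plainly, that score is listed only. Under the protocol's shared label it could be taken as Week 5.

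**The case against.** **The lost pairs are already reported.** The same t-test is run in the Safety and Completer populations, so no usable pair goes unanalysed. Sites telephone patients on the form dates (Protocol Table 1 footnote d), the Week 3 form coincides with the 2-week exposure minimum, the rule is prespecified in both documents, and SAP 5.1.1 treats the test as exploratory. All of this stands and keeps the point small. It does not give a reason for the Week 3 form to decide the lead result.

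**Is the lead population undefined?** A reader might infer this from the SAP 5.2.1 sentence that pairs the evaluable and completer sets. The documents do not support it. SAP 4.2, SAP 5.2.2, Protocol 12.2 and the end of SAP 5.2.1 all make the evaluable set the lead, so the sentence needs only a wording correction.

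**Do patients without Week 5 distort the lead test?** SAP 5.1.5 says "A subject is considered a statistical completer (Evaluable population" and so on, which might suggest that non-completers are counted as completers. The label is unfortunate but is defined where it is used, and such patients add no pair in any population.

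**Will early discontinuation scores be used as Week 5?** A reader might infer this from the protocol's shared label. SAP 5.1.4 most naturally bars such a score when it is outside the window, and Protocol section 12 lets the SAP prevail where the two differ. A real but limited ambiguity remains, because SAP 5.1.4 does not name the visit.

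**Does a new lead set cure dropout bias?** It does not. Once out-of-window early discontinuation scores are barred, treated patients with a usable Week 5 score are nearly the Completer Population. This objection stands in full.

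**Conclusion.** The point holds and is minor. The lead set excludes some valid baseline-to-Week 5 pairs on the strength of a form the endpoint does not use. Each such exclusion below 52 pairs takes the lead test under its stated 80% power (80.3% at 52, 79.5% at 51), given a change of 0.35 and an SD of 0.88.

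Two stronger conclusions are tempting. One is that the study is underpowered. That is not shown, because the rate of missed Week 3 forms is not given and 52 is a minimum. The other is that the current lead set flatters the result. Nothing in the documents fixes the direction in which patients who only missed a home form would move the estimate.

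The correction recovers only the pairs lost to a missed Week 3 form. Selection through dropout stays, and its effect cannot be derived from the documents.

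**What to change.** 1. Make the planned Table 6.5 analysis the primary: all treated patients with valid baseline and Week 5 global scores. Keep Table 6.1 (Evaluable) and Table 6.9 (Completer) as labelled sensitivity analyses. Align SAP 4.2, SAP 5.2.1 and Protocol 12.2.
2. State in SAP 5.1.4 that an early discontinuation score outside Week 5 plus or minus 1 day is out of window and does not enter the primary analysis as Week 5. This confirms the most natural reading of that section.
3. Add one sensitivity analysis in all treated patients with a baseline score, using the last available post-baseline score and including early discontinuation scores. It needs no assignment of those scores to a week. Show the number of treated patients without a usable Week 5 score beside the primary result.

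Step 3 only probes selection through dropout and does not remove it. The cost is wording in the SAP and one protocol section, relabelling of existing tables, one added table and one count row. No new data are needed. The downside is slightly more analysis work.
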